9.4 STATISTICAL ANALYSES

9.4.1 Subject description

9.4.1.1 Disposition of subjects

A detailed description of participant accountability including count of participants by analysis populations ([Table 3](#)), screen failure participants with reasons for screen failure, participants who did not complete the study observation period along with the main reason for permanent treatment discontinuation, and participants who requested permanent treatment discontinuation, will be generated by cohorts.

All withdrawals from the study, taking place on or after study drug intake, will be fully documented in the body of the Clinical Study Report (CSR).

A listing of subjects with treatment discontinuation will be provided.

A listing of all comments related to IMP compliance and dosing, safety (AEs, vital signs), or other comments will be provided by cohorts, participants, visit and examination type in chronological order.

9.4.2 Protocol deviations

During the review of the database, compliance with the protocol will be examined with regard to inclusion and exclusion criteria, treatment compliance, prohibited therapies, and timing and

availability of planned assessments. Protocol deviations will be identified by the study team before database lock and listed in the Data Review and Surveillance Report, including missing data and study drug discontinuations, and classified as critical, major or minor deviations.

Individual deviations to inclusion and exclusion criteria as reported by the Investigator will be listed.

If any, major and critical deviations other than those involving inclusion/exclusion will be listed by participant and/or described in the body of the clinical study report.

9.4.3 Analysis population

The number of participants included in each study population (safety population and efficacy populations (Intent-to-treat and modified-Intent-to-treat)) will be provided. All exclusion from any analysis population will be fully documented in the CSR.

9.4.4 Demographic and baseline characteristics

9.4.4.1 Subject demographic characteristics, medical history and diagnoses

Continuous variables (age, weight) and qualitative variables (gender, race and body mass index [BMI]) will be summarized by cohorts, by descriptive statistics (summary tables) for the mITT population and for additional population if relevant (eg, if many participants from the mITT population are not part of the safety population).

Specific medical/surgical history will be listed. Other baseline characteristics will be listed.

Disease characteristics at baseline: ie, clinical and patient reported outcomes, and skin barrier function, will be presented along with the on-treatment summary statistics in the efficacy [Section 9.4.7](#).

9.4.4.2 Baseline efficacy parameters

Baseline is defined as the last available and evaluable value before and closest to the first dose of the IMP: ie, at D1 (V02, W0), for patients and as the last available and evaluable value at D1 (V02, W0) for healthy volunteers. For TEWL data, the average of the values of the 3 spots within each predefined skin area will be used as baseline, unless a large difference between the spots is observed.

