- g* Peak pruritus NRS and quality of sleep NRS will be assessed daily from Day-7 to Day -1; daily from Day 1 to Day 29 and then for the 7 days prior to Week 6, Week 8, to Week 12 and to Week 16 by e-diary. Patients will bring the eDiary to the site at each visit. eDiary will be reviewed for any questionnaires omission and dispensed back to patients at each visit.
- h* TEWL to be conducted before STS and then after 5, 10, 15, and 20 STS in pre-defined lesional and non-lesional skin. All skin tape strips will be collected and stored.
- i* At Week 0, 8 and 16 STS will be conducted on the first spot within the predefined skin area. At Week 2 STS will be conducted on the second spot within the predefined skin area. At Week 4 and 12 STS will be conducted on the third spot within the predefined skin area. TEWL will be assessed in lesional and non-lesional skin before STS and after 5, 10, 15, and 20 STS. All skin tape strips will be collected and stored for lipidomics, proteomics, and transcriptomics analyses.
- j* Emollients should NOT be applied from Day -7 to the EoT (Week 16, Day 113) to the targeted, pre-defined skin areas that will be used for TEWL assessment. Participants should not take showers or soaking in a bathtub within 6 hours before TEWL assessment. Compliance must be documented in participant's source data. Emollients for use during the study will be provided by the study site to study participants. Use of emollients should be documented in a diary.
- k* Limited to skin-related physical examination at baseline and EoT visit.
- l* Pre-defined lesional (3 spots) and non-lesional skin areas (3 spots), whereby the assessment spots on non-lesional skin are located about 4 cm apart from the edge of the AD lesion.
- m* TEWL will be measured at each of the three closely adjacent spots within the predefined skin areas at all visits as baseline assessment; if there is STS, subsequent TEWL assessment will only be done at the lesional and no-lesional spot, at which STS is performed.
- n* In case STS assessment is to be conducted at an unscheduled visit or at a premature end of treatment visit the assessment should be conducted at that spot of the skin area, for which the period passed since the last STS assessment is the longest.

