8.2.10 Peak Pruritus Numerical Rating Scale (Peak Pruritus NRS)

The Peak Pruritus NRS is a simple assessment tool that patients will use to report the intensity of their pruritus (itch) during a daily recall period. Patients will be asked the following questions:

“On a scale of 0 to 10, with 0 being ‘no itch’ and 10 being the ‘worst itch imaginable’, how would you rate your itch at the worst moment during the previous 24 hours?”

Patients will complete the rating scale daily from Day-7 until Day 29, and then until Day 113 (EoT) at the week before the visits as indicated at [Section 1.3](#).

The Peak Pruritus NRS will be provided in the study reference manual.

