8.2.11 Quality of Sleep NRS

Quality of Sleep NRS to collect information on patient-reported quality of sleep. Numerical rating scale range is from 0 (“worst possible sleep”) to 10 (“best possible sleep”).

Patients will complete the rating scale daily from Day-7 until Day 29, and then until Day 113 (EoT) at the week before the visits as indicated at [Section 1.3](#).

The Quality of Sleep NRS will be provided in the study reference manual.

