1.3 DATA HANDLING CONVENTIONS

This section describes the rules and conventions used in the presentation and analysis of data.

In the statistical appendices and in-text tables, the following cohort label and group label will be used:

- Cohort label:
 - AD patients
 - Healthy volunteers
- Group label:
 - AD patients – lesional skin
 - AD patients – non-lesional skin
 - HV – healthy skin

For parameters with evaluations before administration and in cases of rechecked value(s) for one subject, only the last observation will be used as baseline in descriptive statistics and derivations of other parameter values. After baseline, only observations planned in the protocol will be used in descriptive statistics.

If not otherwise stated in the statistical section of the protocol:

- Missing TEWL data (including data from visits excluded of the efficacy analyses after the use of prohibited medication) will be imputed using Last Observation Carried Forward (LOCF) imputation ; sensitivity analyses will be performed to assess the precision of LOCF imputation versus MMRM imputation.
- Descriptive statistics for quantitative parameters will be provided using number of observations (N), mean, standard deviation (SD), standard error of the mean (SEM), minimum, maximum and median.
- Descriptive statistics for qualitative parameters will be provided using frequencies (N) and percent (%).

Handling missing data for adverse events

In case of missing or inconsistent information on the time of onset, an AE will be counted as a treatment-emergent adverse event (TEAE) unless it can clearly be ruled out that it is not a TEAE (eg, by partial dates or other information).

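### The baseline for peak pruritus NRS and sleep NRS is one diary day although a week of daily entries is collected, and the post-baseline score is not defined

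*Protocol*

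**What the plan says.** **Collection.** Protocol 1.3, footnote g, has patients score both scales every day in the week before baseline and through the first four weeks of treatment. After that the diary runs only in blocks: "and then for the 7 days prior to Week 6, Week 8, to Week 12 and to Week 16 by e-diary". Protocol 8.2.10 asks about peak itch over one day: "how would you rate your itch at the worst moment during the previous 24 hours". Protocol 8.2.11 gives the sleep scale the same daily schedule ("Patients will complete the rating scale daily from Day-7 until Day 29") but states no recall window.

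**Baseline.** Protocol 9.4.4.2: "Baseline is defined as the last available and evaluable value before and closest to the first dose of the IMP", which the section places at Day 1 for patients. Its only averaging provision is over spots, not days, and is for another measure: "For TEWL data, the average of the values of the 3 spots within each predefined skin area will be used as baseline", unless the spots differ widely. SAP 1.3, in a sentence that also deals with rechecked values, says that "only the last observation will be used as baseline in descriptive statistics and derivations of other parameter values".

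**Use.** Protocol Table 4 summarises absolute and percent change in both scales by time point. It plans Pearson correlations with TEWL before stripping and with TEWL AUC at baseline, Week 8 and Week 16, including correlations of change from baseline.

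**Absent.** Neither document gives a weekly mean, a diary window or a minimum number of completed days for either scale, at baseline or later.

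**The concern.** Patients are asked for a week of daily scores before treatment, and the stated rule uses one of the values available. A single day's worst itch or sleep rating carries day-to-day variation that a weekly mean would largely remove. That variation enters every change score, because all of them share the same baseline. It also pulls the baseline correlations with TEWL towards zero, and the Week 8 and Week 16 correlations of change inherit it.

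The post-baseline side is open. Table 4 refers to time points but does not say which diary entries make up Week 8 or Week 16. A programmer could reasonably average the 7-day block there while following 9.4.4.2 at baseline. The two ends of the change score would then be different quantities.

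Percent change is exposed as well. On the sleep scale, 0 is the worst score, so one very bad night at baseline can give a zero denominator.

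At stake is one exploratory objective, the association of barrier function with patient-reported outcomes. In about 20 patients, a real association with itch or sleep could look weaker than it is.

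**Working it through.** **1. The plan's own figure.** Protocol 9.2 seeks 20 evaluable patients with 15% drop-out: 20 / (1 − 0.15) = 23.53, rounded up to 24. This reproduces and does not depend on the NRS. It supplies n = 20 below. The documents state no precision or reliability for either scale.

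**2. Which entry is the baseline?** Section 9.4.4.2 points to Day 1. The schedule marks both scales at that visit. Protocol 8.2.3 has the NRS completed before TEWL at each visit, and footnote c of Protocol 1.3 puts those skin assessments before dosing. The last pre-dose value is therefore probably the Day 1 entry. If so, none of the seven entries from Day -7 to Day -1 is used. If Day 1 has no pre-dose entry, the most recent of the seven is used and the others are not.

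**3. Effect on a baseline correlation.** Assumptions: single-day reliability r between 0.6 and 0.8, and independent daily errors. TEWL's own error is the same either way and is left out.
- Reliability of a 7-day mean: 7r / (1 + 6r).
- Attenuation of a correlation: square root of the reliability.
- Ratio, one day to 7-day mean: √r / √[7r / (1 + 6r)] = √[(1 + 6r) / 7].

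| r | 7-day reliability | Attenuation, one day | Attenuation, 7-day mean | Ratio |
|---|---|---|---|---|
| 0.6 | 0.913 | 0.775 | 0.956 | 0.81 |
| 0.7 | 0.942 | 0.837 | 0.971 | 0.86 |
| 0.8 | 0.966 | 0.894 | 0.983 | 0.91 |

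For an assumed true correlation of 0.50, the expected observed values are 0.39, 0.42 and 0.45 with one day, and 0.48, 0.49 and 0.49 with the 7-day mean. Approximate power at n = 20 (Fisher z, two-sided 0.05) is 39%, 45% and 51% against 57%, 59% and 60%.

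**4. If daily errors are serially correlated.** With independent errors, a single day's error variance is k = 7 times that of the mean. With first-order autocorrelation φ, k = 49 / [7 + 2Σ(7 − j)φ^j], with j from 1 to 6. This gives 4.16, 2.88 and 1.93 for φ = 0.3, 0.5 and 0.7. The ratio in step 3 becomes √[r + (1 − r) / k]. At r = 0.7 it is 0.88, 0.90 and 0.92, against 0.86 under independence.

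**5. Effect on a change score.** Let e = 1 − r be the error share of the single-day variance, with independent errors. The error SD of change, in units of the single-day SD at r = 0.7, is:
- one day at both ends: √(2e) = 0.775
- one day at baseline, 7-day mean later: √(e + e/7) = 0.586
- 7-day means at both ends: √(2e/7) = 0.293

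The mixed case has exactly twice the error SD of the matched 7-day case at any r, since √[(8/7) / (2/7)] = 2. In scale points, taking a between-patient SD of 2 as a further assumption, the error variance is 4 × 0.3 / 0.7 = 1.714. The three SDs are then 1.85, 1.40 and 0.70.

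**The case against.** The strongest case against is that this matters little here. Both scales are exploratory, no hypothesis is predefined, and the sample size dominates the uncertainty. At r = 0.7 the two expected correlations, 0.42 and 0.49, have 95% intervals at n = 20 of −0.03 to 0.73 and 0.06 to 0.77, which overlap almost entirely. This stands. It limits the importance of the point but gives no reason to leave collected data unused.

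A second argument favours Day 1: that score is taken on the same day as the TEWL it is correlated with. This is a fair reason to keep a same-day correlation. The documents do not offer it as their reason. It also does not serve the change summaries.

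A third is that the diary week falls in the topical washout (exclusion criterion E 07). If itch drifts over that week, a 7-day mean need not equal the level at first dose. The documents do not say whether it drifts; the daily values would show it.

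Two stronger readings are tempting, and neither is supported:
- A reader might infer that single days are used after baseline as well and that the later 7-day blocks play no part. Section 9.4.4.2 governs baseline only. SAP 1.3 admits protocol-planned observations after baseline, and the diary blocks are planned. Their handling is undefined, not single-day.
- A reader might take the SAP sentence as a separate ruling on diary data. It is a general convention that also covers rechecked values. The point rests on Protocol 9.4.4.2.

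**Conclusion.** The point holds for two exploratory scales. As written, the NRS baseline is one diary entry, the preceding diary week is unused, and the post-baseline score is undefined. The change score may therefore compare unlike quantities.

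The size cannot be taken from the documents. At an assumed single-day reliability of 0.6 to 0.8 with independent daily errors, a baseline correlation with TEWL is 81% to 91% of its value with a 7-day mean. The sevenfold difference in error variance belongs to that independence assumption and is an upper figure if errors are positively correlated from day to day. The 24-hour recall is explicit for itch only.

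A reader might infer that the study's main conclusions are at risk. They are not: the primary and secondary endpoints are TEWL measures, and neither they nor the sample size depends on these scales. The change is worth making because it is nearly free and settles a derivation that would otherwise be chosen with open-label data in hand.

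**What to change.** Add to the SAP, before database lock:
- **Baseline** for peak pruritus NRS and sleep NRS: the mean of the daily values in the 7 days before first dose. Choose either Day -7 to Day -1, or the last seven pre-dose entries if the pre-dose Day 1 entry is to count. State a minimum number of completed days, for example 4 of 7.
- **Post-baseline score from Week 2 on**, including Weeks 8 and 16: the mean of the 7 days before the visit, with the same minimum.
- **Visits before Week 2**: use post-dose days only, or show the daily values in the profile plot. A 7-day window before the nominal Day 8 visit covers Days 1 to 7 and so takes in the pre-dose Day 1 entry. A visit at Day 6, within the ±2-day window, would also take in Days -1 and -2.
- **Use** these means in the change summaries and the TEWL correlations.
- **Sensitivity analysis**: keep the correlation of the Day 1 NRS with the Day 1 TEWL, since the weekly mean gives up the same-day match.

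The cost is a few lines of SAP text and one derived variable per scale. No new data are needed. The 4-of-7 minimum is a suggestion; the documents give no figure.

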9.4.4.3 Baseline safety parameters

Baseline for safety parameters will be defined as the last available and evaluable value before and closest to the first dose of IMP for patients and as the last available and evaluable value at D1 (V02, W0) for healthy volunteers, for vital sign parameters.

Baseline safety values will be presented along with subsequent safety values assessed during the study.

9.4.5 Extent of study treatment exposure and compliance

The extent of study treatment exposure and compliance will be assessed and summarized for patients' cohort within the safety population.

The following listings will be provided:

- Patients receiving IMP from specified batch; (patient, drug product batch number, drug product) will be sorted by patient.

9.4.5.1 Extent of investigational medicinal product exposure

Duration of IMP exposure is defined as: last dose date – first dose date + 14 days, regardless of unplanned intermittent discontinuations.

If the patient's date of last dose is unknown, his/her last IMP dispensing date will be used in its place.

Duration of exposure will be summarized in patients' cohort using descriptive statistics such as mean, standard deviation (SD), median, minimum and maximum.

9.4.5.2 Compliance

A given administration will be considered noncompliant if the patient did not take the planned dose of treatment as required by the protocol. No imputation will be made for patients with missing or incomplete data.

Percentage of compliance for a patient will be defined as the number of administrations the patient was compliant divided by the total number of administrations the patient was planned to take (the number of doses missed due to interruptions at investigators' judgment will not be subtracted) on or before the last IMP administration date.

Treatment compliance, above-planned and under-planned dosing percentages will be summarized descriptively (N, mean, SD, median, minimum, and maximum). The percentage of patients with compliance <80% will be summarized. In addition, number and percentage of patients with at least 1 above-planned dosing administration will be given, as well as the number and percentage of patients with 0, (0, 20%], and >20% under-planned dosing administrations.

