1.3 SCHEDULE OF ACTIVITIES (SOA) / AD PATIENTS

Phase	Screening	Baseline	Treatment Phase										EoT	EoS ^a	Un-scheduled Visit	Premature EoT
Day	D-28 to D-1	D 1	D4 ±2 days	D8 ±2 days	D11 ±2 days	D15 ±2 days	D22 ±2 days	D29 ±2 days	D43 ±2 days	D57 ±3 days	D85 ±3 days	D113 ±3 days	D141 ±3 days	UNSCH		
Week		W0		W1		W2	W3	W4	W6	W8	W12	W16	W20			
Visits	V01	V02	V03	V04	V05	V06	V07	V08	V09	V10	V11	V12	V13			
Informed consent / assent form	X															
Inclusion/exclusion criteria	X	X														
Medical/surgical history / IGA / Demographics	X															
Prior/concomitant medications / procedures	X	X	X	X	X	X	X	X	X	X	X	X	X	X	X	
Confirm emollient and washing compliance ^j	X	X	X	X	X	X	X	X	X	X	X	X		X	X	
Study treatment administration																
SC administration of dupilumab ^b		X				X		X	X	X	X			(X)		
Study drug self-administration training by site staff ^o										X				(X)		
Study drug will be handed out at V10 (Week 8) for self-administration at Week 10 and at V11 (Week 12) for self-administration at Week 14										X	X			(X)		
Compliance check of self-administered study drug at Week 10 and Week 14											X	X		(X)	X	

Phase	Screening	Baseline	Treatment Phase										EoT	EoS ^a	Un-scheduled Visit	Premature EoT
Day	D-28 to D-1	D 1	D4 ±2 days	D8 ±2 days	D11 ±2 days	D15 ±2 days	D22 ±2 days	D29 ±2 days	D43 ±2 days	D57 ±3 days	D85 ±3 days	D113 ±3 days	D141 ±3 days	UNSCH		
Week		W0			W1		W2	W3	W4	W6	W8	W12	W16	W20		
Visits	V01	V02	V03	V04	V05	V06	V07	V08	V09	V10	V11	V12	V13			
Skin barrier function test in lesional and non-lesional skin^c																
TEWL at baseline/ before STS ^{l,m}		X	X	X	X	X	X	X	X	X	X	X	X		(X)	X
TEWL after STS assessment ^h		X ⁱ				X ⁱ		X ⁱ		X ⁱ	X ⁱ	X ⁱ			(X) ⁿ	X ⁿ
Lipidomics, filaggrin (FLG) breakdown products, proteomics, and transcriptomics assessment from skin tape strip ⁱ		X ⁱ				X ⁱ		X ⁱ		X ⁱ	X ⁱ	X ⁱ			(X) ⁿ	X ⁿ
Standardized photographs of lesional and non-lesional skin areas used for TEWL ^l		X	X	X	X	X	X	X	X	X	X	X			(X)	X
Standardized full body photographs		X	X	X	X	X	X	X	X	X	X	X			(X)	X
EASI	X	X	X	X	X	X	X	X	X	X	X	X			(X)	X
ISS on lesion erythema and edema/papulation	X	X	X	X	X	X	X	X	X	X	X	X			(X)	X
SCORAD	X	X	X	X	X	X	X	X	X	X	X	X			(X)	X
Patient reported outcomes (PRO)																
POEM		X		X		X	X	X	X	X	X	X			(X)	X
DLQI/CDLQI ^f		X		X		X	X	X	X	X	X	X			(X)	X
Peak pruritus NRS ^g		X	X	X	X	X	X	X	X	X	X	X			(X)	X

Phase	Screening	Baseline	Treatment Phase									EoT	EoS ^a	Un-scheduled Visit	Premature EoT

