6.1 STUDY INTERVENTION(S) ADMINISTERED

Study participants will be assigned to study intervention as described below:

- Up to 24 adolescent and adult moderate to severe AD patients will receive dupilumab.
- For AD patients aged ≥ 12 to < 18 years the dose regimen will follow the table below and based on the body weight on Day 1 (the dose will not be changed during the study):

Body Weight	Loading Dose on Day 1	Subsequent Doses (Q2W)
less than 60 kg	400 mg (two 200 mg injections)	200 mg
60 kg or more	600 mg (two 300 mg injections)	300 mg

- AD patients age 18 years and older will receive a SC loading dose of 600 mg on Day 1, followed by 300 mg Q2W SC through Week 14. Drug will be administered by study site staff at baseline, Weeks 2, 4, 6, 8, 12. Drug will be self-administered by AD patients at Week 10 and 14.

One kit number list by dosage strength is generated centrally by Sanofi and IMP are packaged in accordance with these lists. The treatment will be given to the patient depending on their age and body weight.

Study intervention will be dispensed at the study visits summarized in SoA (see [Section 1.3](#)). Returned study intervention should not be re-dispensed to the participants.

Table 2 - Overview of study interventions administered

ARM name	Dupilumab 200	Dupilumab 300
Intervention name	Dupilumab 200 mg	Dupilumab 300 mg
Type	Biological/Vaccine	Biological/Vaccine
Dose formulation	A 175 mg/mL dupilumab solution in a pre-filled syringe to deliver 200 mg in 1.14 mL	A 150 mg/mL dupilumab solution in a pre-filled syringe to deliver 300 mg in 2 mL
Unit dose strength(s)	200 mg	300 mg
Dosage level(s)	200 mg every 14 \pm 2 or 3 days after an initial loading dose of 400 mg	300 mg every 14 \pm 2 or 3 days after an initial loading dose of 600 mg
Route of administration	Subcutaneous ^a	Subcutaneous ^a
Use	Experimental	Experimental
IMP	IMP	IMP

ARM name	Dupilumab 200	Dupilumab 300
Packaging and labeling	One glass pre-filled syringe packed in a patient kit box. Both the glass pre-filled syringe and the box will be labeled as required per country requirement.	One glass pre-filled syringe packed in a patient kit box. Both the glass pre-filled syringe and the box will be labeled as required per country requirement.
[Current/Former name(s) or alias(es)]	Dupixent®	Dupixent®

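### The compliance percentage stops counting planned doses at the last dose given, so a skipped Week 14 home dose still scores 100%

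*Protocol*

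**What the plan says.** **Compliance (Protocol 9.4.5.2).** At the level of a single dose, "A given administration will be considered noncompliant if the patient did not take the planned dose of treatment as required by the protocol". The patient's percentage is "defined as the number of administrations the patient was compliant divided by the total number of administrations the patient was planned to take", and the denominator is then limited by the words "will not be subtracted) on or before the last IMP administration date". The closing bracket ends an aside that keeps doses missed through investigator-directed interruptions in the denominator. Two categorical summaries follow: "The percentage of patients with compliance <80% will be summarized", and the "number and percentage of patients with 0, (0, 20%], and >20% under-planned dosing administrations".

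**Exposure (Protocol 9.4.5.1).** Duration is the last dose date minus the first dose date plus 14 days. If the last dose date is unknown, "his/her last IMP dispensing date will be used in its place".

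**Dosing schedule (Protocol 1.3 and 6.1).** "Drug will be administered by study site staff at baseline, Weeks 2, 4, 6, 8, 12"; Weeks 10 and 14 are for self-injection. The second home kit is handed out "at V11 (Week 12) for self-administration at Week 14".

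**SAP.** Section 1.1 refers back to Section 9 of the protocol for the methods. Sections 1.2 and 1.3 change neither rule.

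**The concern.** A missed dose should cost the same wherever it falls in the schedule. Under this denominator it does not: a dose missed mid-course is counted only because a later dose was given, and a dose missed at the end disappears. The aside about interruptions fails for the same reason. It says such doses stay in, yet an interruption with no later dose takes them out.

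The position affected is an awkward one. Week 14 is the last dose before the Week 16 primary measurement and one of only two planned outside the clinic. The study has no treatment control group in patients (Protocol 6.3) and measures no drug levels (Protocol 8.6), so dosing records are the evidence that drug was received. A compliance table that reads 100% for a patient who skipped the last dose describes treatment up to the endpoint wrongly.

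The exposure fallback has a smaller fault at the same place. A date is most likely to be unknown for a home dose, because the date and time of clinic doses are recorded (Protocol 6.4). Home kits are handed out two weeks before they are due.

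**Working it through.** **Inputs.** Planned dosing days are 1, 15, 29, 43, 57, 71, 85 and 99 (Protocol 1.3, dosing footnote), so eight doses. Home doses fall on Day 71 (Week 10) and Day 99 (Week 14). The kits are dispensed on Day 57 and Day 85. The visit and dosing windows on these four days are ±3 days.

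**Reproducing the plan's own figure.** Full regimen: exposure = 99 − 1 + 14 = 112 days = 16 weeks, which agrees with the 16 weeks of treatment stated in Protocol 2.3.2.

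**Compliance.** As written: compliant doses ÷ doses planned up to the day of the last dose given. Against plan: compliant doses ÷ 8. All doses not listed as missed are taken to be compliant.

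| Missed | As written | Against plan | Exposure (days) |
|---|---|---|---|
| None | 8/8 = 100% | 8/8 = 100% | 112 |
| Week 10 | 7/8 = 87.5% | 7/8 = 87.5% | 112 |
| Week 14 | 7/7 = 100% | 7/8 = 87.5% | 85 − 1 + 14 = 98 |
| Weeks 10 and 14 | 6/7 = 85.7% | 6/8 = 75% | 98 |
| Weeks 12 and 14 | 6/6 = 100% | 6/8 = 75% | 71 − 1 + 14 = 84 |

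**Effect on the below-80% count.** Missing Week 14 alone changes nothing: both 100% and 87.5% are above 80%. The last two rows do change it, since 75% is below 80% and neither written figure is. The Weeks 12 and 14 row assumes that no definitive discontinuation was recorded.

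**Effect on the under-planned categories.** The protocol does not give the denominator for these. If it is the same one and a missed dose counts as under-planned, missing Week 14 alone is 0/7 = 0% as written and 1/8 = 12.5% against plan, so the patient sits in the zero category instead of the (0, 20%] category.

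**Exposure fallback.** Week 14 dose taken, date unknown: Day 85 replaces a nominal Day 99, which is 14 days early. Within the windows the gap runs from (99 − 3) − (85 + 3) = 8 to (99 + 3) − (85 − 3) = 20 days. Exposure becomes 98 instead of 112 days (14/112 = 12.5% short), the same value as for a patient who never took the dose. If Week 10 is the last dose and its date is unknown, the result is 57 − 1 + 14 = 70 instead of 71 − 1 + 14 = 84 days. One such patient among 24 shifts mean exposure by 14/24 ≈ 0.6 days.

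**The case against.** The cut-off can be defended as deliberate. Compliance then describes adherence while dosing continues, and early stopping is shown by exposure duration and disposition. For a patient who definitively stops treatment this is reasonable and should be kept. It does not cover a patient who stays on treatment and skips the last dose, and the formula does not separate the two.

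The stronger part of the objection concerns consequences. A reader might infer that a weak Week 16 result could not be told apart from failure to take the drug. The documents do not support that:

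- Exposure shows the skip (98 against 112 days) when dates are known.
- The schedule of activities places a check of the Week 14 home dose at Week 16.
- Protocol 6.4 requires a count of unused syringes, a home dosing diary and entry of dosing deviations in the eCRF.
- Protocol 9.4.1.1 lists comments on dosing by participant, and 9.4.2 reviews treatment compliance before database lock.

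With about 24 patients, each missed Week 14 dose can be found.

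Nor does either formula reach the efficacy results. Neither the mITT nor the ITT population (Protocol 9.3, SAP 1.2) is defined by percent compliance.

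The two-dose examples are also less likely than a single skip. Missing Week 12 means missing a clinic dose at the visit that supplies the Week 14 kit, and Protocol 7.1 requires definitive and temporary discontinuations to be recorded. The date fallback should be rare given the diary and the Week 16 check, patients may choose to be injected at the site (Protocol 6.1), and its error shortens reported exposure, so it does not flatter the trial.

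All of this stands as a limit on the harm. It does not make 7/7 the right score for a patient who took seven of eight planned doses.

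**Conclusion.** The point holds as a definite but contained fault in a descriptive summary. Taking the cut-off to be the last dose actually given, and all other doses as compliant, a skipped Week 14 dose is reported as 100% instead of 87.5%, while the same skip at Week 10 is reported as 87.5%. The below-80% count is wrong only when at least two doses including the last are missed. The effect on the under-planned categories depends on a denominator that the protocol does not state.

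The primary TEWL analysis is untouched, and the missed dose remains visible in exposure duration and in patient-level records. The exposure fallback is secondary: nominally 14 days too early for a home dose, probably seldom used, but when used it makes a dose that was taken look the same as one that was not.

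**What to change.** **Section 9.4.5.2.** Define the denominator as administrations planned up to the earlier of the EoT visit and the recorded date of definitive discontinuation. This keeps the cut-off for patients who stop, counts every other dose missed at the end, and makes the aside on interruptions hold throughout. State that the under-planned percentages use the same denominator.

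**Section 9.4.5.1.** When a home dose is known to have been taken but its date is unknown, use the scheduled dosing day (Day 71 or Day 99), bounded by the next visit, for the exposure calculation only.

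**Optional.** Report the number and percentage of patients who received the Week 14 dose.

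**Cost.** A few sentences in the SAP and minor programming. The data are already collected through the diary, syringe accountability and the Week 16 check. No dosing or clinical rule changes. The downside is that reported compliance may be slightly lower.
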